5.2 Analysis Sets

The following analysis sets are defined for this interim analysis:

Safety Population: All participants who receive Study vaccine in ARCT-021-02 only.

Longitudinal Safety Population: All participants who receive Study vaccine in either ARCT-021-01 or ARCT-021-02

Immunogenicity Population: All participants who receive Study vaccine in either ARCT-021-01 or ARCT-021-02 and who have evaluable immunogenicity data following first vaccine administration.

Within these populations, analyses will also include Cohorts that combine relevant safety and immunogenicity assessments across ARCT-021-01 and ARCT-021-02 according to time since administration of last dose of ARCT-021. These cohorts are defined as follows.

Two primary cohorts will be defined:

- Cohort 1: ARCT-021-02 vaccinated participants (those participants who receive ARCT-021 in Study ARCT-021-02, including those who were assigned to receive placebo in the parent study (ARCT-021-01) and those who enter the ARCT-021-02 without detectable neutralizing antibody responses at baseline)

This cohort will be further subdivided into additional sub-cohorts for all analyses:

- Cohort 1a: Primary vaccination (i.e., those participants whose first ARCT-021 vaccine administration occurs in the ARCT-021-02 study) and
- Cohort 1b: Booster vaccination (i.e., those participants who received primary vaccination in the ARCT-021-01 study and who receive an additional dose of ARCT-021 in the ARCT-021-02 study). Cohort 1b will be subdivided as follows for data analysis and presentation:
 - Cohort 1b (A): Participants that were in Cohort A (1 mcg single dose younger adult cohort) in the Parent Study
 - Cohort 1b (B): Participants that were in Cohort B (5 mcg single dose younger adult cohort) in the Parent Study
 - Cohort 1b (C): Participants that were in Cohort C (10 mcg single dose younger adult cohort) in the Parent Study
 - Cohort 1b (D1): Participants that were in Cohort D1 (7.5 mcg single dose younger adult cohort) in the Parent Study
 - Cohort 1b (D2): Participants that were in Cohort D2 (7.5 mcg single dose older adult cohort) in the Parent Study

- Cohort 2: ARCT-021-01 vaccinated participants (i.e., those participants who were vaccinated with ARCT-021 in the parent study and who do not receive subsequent vaccination with ARCT-021 in the current extension study). Cohort 2 will be subdivided as follows for data analysis and presentation:

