For unsolicited AEs (AEs), the following will be summarized and presented at the time of final analysis for the safety and longitudinal safety population:

- i. An overall summary of TEAEs, by cohort/sub-cohort and age groups, which includes the following:
 - a. The number and percentage of participants experiencing a TEAE
 - b. The number and percentage of participants experiencing a TEAE by strongest relationship to study medication ('Related to study vaccine' vs 'Not Related'). Relationship will be determined as described in Section 8.1.3.
 - c. The number and percentage of participants experiencing a TEAE by maximal severity.
 - d. The number and percentage of participants experiencing a Related TEAE by maximal severity.
 - e. The number and percentage of participants experiencing a TEAE leading to withdrawal from study.
 - f. The number and percentage of participants experiencing a TEAE leading to death
 - g. The number and percentage of participants experiencing a treatment emergent SAE
 - h. The number and percentage of participants experiencing a treatment emergent MAAE
 - i. The number and percentage of participants experiencing NOCD
- ii. The number and percentage of participants experiencing a TEAE by SOC and PT, by age group and cohort/sub-cohort.
- iii. The number and percentage of participants experiencing a TEAE by SOC, PT and the relationship to study medication, by age group and cohort/sub-cohort.
- iv. The number and percentage of participants experiencing a related TEAE by SOC, PT and the maximal severity, by age group and cohort/sub-cohort.
- v. The number and percentage of participants experiencing a TEAE by SOC, PT, and maximal severity, by age group and cohort/sub-cohort.

The treatment emergent SAEs, MAAEs, NOCDs and AE leading to discontinuation/withdrawal will be listed.

The age groups referenced above are all participants, 21 to 55 years, and 56 to 80 years at the time of enrolment in the Parent Study. The cohort/sub-cohorts are described in Section 5.2

In the overall summary of TEAEs, Table (i), besides tabulating the number and percentage of participants, the total number of TEAE episodes will also be provided. If a participant has repeated

occurrences of a particular TEAE, all episodes will be counted in the occurrences.

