In the remaining summary tables, the incidence of TEAEs will be calculated by dividing the number of participants who have experienced the event by the total number of participants in the corresponding Cohort. Thus, the incidence of TEAEs is shown in terms of the total number of participants and not in terms of the total number of episodes. If a participant has repeated episodes of a particular TEAE, only the most severe episode, or the episode with the strongest causal relationship to study vaccine, will be counted in the summary tables.

A participant with more than one type of TEAE in a particular SOC will be counted only once in the total of participants experiencing TEAEs in that particular SOC, but all PTs for that participant will be shown. Since a participant could have more than one type of TEAE within a particular SOC, the sum of participants experiencing different TEAEs within the SOC could appear larger than the total number of participants experiencing TEAEs in that SOC. Similarly, a participant who has experienced a TEAE in more than one SOC will be counted only once in the total number of participants experiencing AEs in all SOCs.

All occurrences of all TEAEs will be listed for each participant, grouped by cohort. The listing will contain the following information: treatment group, verbatim term, SOC, PT, severity, relationship to study medication, date and day of onset, date and day of resolution, treatment given to treat the adverse event, the outcome, whether the event was an SAE and/or a MAAE and/or NOCD, and whether it led to withdrawal. Listings will be sorted by participant identification number, onset date, SOC, and PT. If the onset date is completely missing, then these events will be presented first. If the onset date is missing a month or a day, then these events will be presented before any complete dates.

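### As written, SAP 8.1.9.1 divides TEAE counts by the whole cohort in Tables (ii) to (v), so in mixed-age cohorts the age-group percentages are not age-specific rates

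*SAP*

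**What the plan says.** SAP 8.1.9.1 lists five displays of unsolicited events. Table (i) is an overall summary. Tables (ii) to (v) break TEAEs down by system organ class and preferred term, with relationship or severity added in (iii) to (v). All are split by age; Table (ii), for example, is "The number and percentage of participants experiencing a TEAE by SOC and PT, by age group and cohort/sub-cohort". The age categories are then fixed: "The age groups referenced above are all participants, 21 to 55 years, and 56 to 80 years at the time of enrolment", where enrolment means entry to the Parent Study.

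The denominator rule follows. It applies to the tables left after Table (i), and each percentage there is found by "dividing the number of participants who have experienced the event by the total number of participants in the corresponding Cohort". The sentence after it explains that incidence therefore counts people and not episodes. Neither sentence mentions age group, and no other part of the SAP gives an age-specific denominator. Table (i) is dealt with just before this rule and falls outside it.

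SAP 5.2 defines the cohorts by vaccination history. Cohort 1a is "those participants whose first ARCT-021 vaccine administration occurs in the ARCT-021-02 study" and is not divided by age. Cohorts 1b and 2 are divided by Parent Study cohort, and each of those is a single age band. One example is "Participants that were in Cohort D1 (7.5 mcg single dose younger adult cohort) in the Parent Study"; its older counterpart is "Participants that were in Cohort D2 (7.5 mcg single dose older adult cohort) in the Parent Study".

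**The concern.** A percentage in an age column is read as the risk in that age group. If the divisor is everyone in the cohort, the two age percentages instead add up to the all-ages percentage. Each then shows how much of the cohort's incidence came from that age group, and the contrast between ages partly reflects how many people of each age enrolled. When the groups differ in size, the smaller one looks safer than it is relative to the larger.

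Unsolicited events by severity and relationship are among the primary safety endpoints (SAP 8), the analysis is descriptive (SAP 5), and the interim supports a regulatory filing (SAP 4). The percentages are therefore the main safety result a reader sees. Double programming (SAP 5.1) does not protect against this. Two programmers who apply the written rule will agree on the same figure, and two who read it differently have no text to settle the mismatch.

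**Working it through.** The SAP states no figure for this point, so there is nothing to reproduce. The check is to apply the written rule and compare it with a within-age denominator.

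**Where ages can mix (SAP 5.2)**
- Pooled Cohort 1b: A, B, C and D1 are younger; D2 is older.
- Pooled Cohort 2: A, B, C, D1, E and F are younger; D2, G and H are older.
- Cohort 1a: age mix not stated. Pooled Cohort 1 combines 1a and 1b.
- Each lettered sub-cohort: one age band only.

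SAP 3.1 gives a possible total of 106 participants, with no breakdown by cohort and age. The older share below is therefore an assumption, shown over a range.

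**Formula.** Let N be the cohort size, f the older share and p the true risk, equal in both age groups.
- Older cases = p × f × N. Divided by N, the table shows p × f.
- Younger cases = p × (1 − f) × N. Divided by N, the table shows p × (1 − f).
- The two sum to p, the all-participants percentage.
- With the age group as denominator, both rows show p.

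**Results for an assumed p = 20%**

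| Older share f | Younger, as written | Older, as written | Ratio | Both, within-age denominator |
|---|---|---|---|---|
| 20% | 16.0% | 4.0% | 4.00 | 20.0% |
| 30% | 14.0% | 6.0% | 2.33 | 20.0% |
| 40% | 12.0% | 8.0% | 1.50 | 20.0% |
| 50% | 10.0% | 10.0% | 1.00 | 20.0% |

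**In counts (assumed).** Take 20 younger and 10 older participants with 8 and 4 cases. Within age, 8/20 = 4/10 = 40%. As written, 8/30 = 26.7% and 4/30 = 13.3%.

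**Two consequences**
- The older percentage cannot exceed f. With f = 30%, it reads 30% even if every older participant has the event.
- A real difference can be hidden. With f = 30%, an older risk that is 0.7/0.3 = 2.33 times the younger risk gives equal percentages in the two rows.

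**Where nothing changes.** In a single-age sub-cohort the age group is the whole sub-cohort, so the two denominators coincide. In the all-participants rows the cohort total is the right divisor.

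**The case against.** The best reply is that the sentence was never meant to set an age denominator. Its stated purpose is to count participants rather than episodes, and 'corresponding' can be read as the matching table column. Protocol 10.5.1 calls for clinical data to be summarised separately by age group, and Protocol 10.5.5 says much the same for clinical events of special interest; a separate summary naturally uses that group's own N. Column Ns may also be in the table shells mentioned in SAP 5.1, which are not in the documents. Counts are printed beside the percentages, TEAEs are listed by participant, and no hypothesis is tested.

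Most of this stands as evidence of intent. It does not supply a different denominator: 'Cohort' is defined in SAP 5.2, and none of its definitions is an age group within a mixed cohort.

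Several stronger readings are tempting, and the documents do not support them:
- *That the tables were or will be miscalculated.* Only the text is available, and loose wording is a plausible explanation.
- *That age-specific rates are understated throughout.* All-participants rows and single-age sub-cohorts are not affected. The SAP labels the sub-cohorts as Cohorts in their own right, such as Cohort 1b (D2), so dividing D2 events by a pooled cohort in D2's own column is not a natural reading.
- *That equal risks always look different, or that older adults always look safer.* This depends on which age group is smaller, and at 50:50 there is no false contrast.
- *That Table (i) and the solicited tables carry the same wrong rule.* They lie outside the sentence and state no denominator.

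**Conclusion.** The concern holds in limited form. For Tables (ii) to (v), the rule as written gives shares of cohort incidence instead of age-specific rates in pooled Cohorts 1, 1b and 2, and in Cohort 1a if it contains both ages. With equal true risk, the ratio between the age rows is (1 − f)/f: from 4.00 at an older share of 20% to 1.00 at 50%, where both rates are halved. These sizes rest on assumed age splits and an assumed 20% risk; the documents give neither. The effect is on how descriptive tables read and on no error rate. It is a defect in the specification and does not show an error in the output.

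**What to change.** Replace the denominator in SAP 8.1.9.1 with: the number of participants in the same analysis population, cohort/sub-cohort and age group (the column N). Print that N at the head of each column. For consistency, state the same denominator for the age columns of Table (i) and of table (ii) in SAP 8.1.9.2.

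The cost is one sentence and column Ns in the shells, with no new data. If the sponsor already intended this calculation, only the text changes. SAP 5.1 bars changes after the data pull, so the wording should be settled before then.

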8.1.9.2 Solicited Events with Onset Within 7 Days of Injection

Solicited events are reactogenic events that are recorded in the symptom diary together with a participant attributed grade. These are classified as follows:

- Solicited local events: pain, tenderness, erythema or swelling at the injection site
- Solicited systemic events: fever, fatigue, headache, chills, nausea, vomiting, diarrhea, myalgia, and arthralgia

The severity of solicited events will be graded by the participant according to the Toxicity Grading Scale for Healthy Adult and Adolescent Volunteers Enrolled in Preventive Vaccine Clinical Trials, Sept 2007.

For solicited events, the following will be summarized and presented at the time of final analysis for the safety population,

- i. An overall summary of all solicited adverse events with onset on or before 7 days after injection of study vaccine, for Safety Population, by cohort/sub-cohort, which includes:
 - a. the number and percentage of participants experiencing a solicited event summarized by cohort/sub-cohort.

- b. the number and percentage of participants experiencing a solicited local event summarized by cohort/sub-cohort.
- c. the number and percentage of participants experiencing a solicited systemic event summarized by cohort/sub-cohort.
- d. the number and percentage of participants experiencing a solicited event by maximal severity and by cohort/sub-cohort
- e. the number and percentage of participants experiencing a solicited local event by maximal severity and by cohort/sub-cohort
- f. the number and percentage of participants experiencing a solicited systemic event by maximal severity and by cohort/sub-cohort
- g. the number and percentage of participants experiencing a solicited event leading to withdrawal from study by cohort/sub-cohort
- h. the number and percentage of participants experiencing a solicited local event leading to withdrawal from study by cohort/sub-cohort
- i. the number and percentage of participants experiencing a solicited systemic event leading to withdrawal from study
- j. the number and percentage of participants experiencing a serious solicited event by cohort/sub-cohort
- ii. the number and percentage of participants experiencing a solicited event by Systemic vs Local and by event term, day post vaccination (from Day 1 to Day 7, where Day 1 is the day of injection), by age groups, and the maximal severity. The number and percentage of participants experiencing a solicited event, by event term, by age group, occurring at any time from Day 1 to Day 7 will also be displayed.

The age groups referenced above are all participants, 21 to 55 years, and 56 to 80 years at the time of enrollment in the Parent Study. Cohort/sub-cohorts are described in Section [5.2](#).

8.1.9.3 Adverse Events After Off-Study Vaccine.

- i. An overall summary of unsolicited treatment emergent adverse events with onset after injection of off-study vaccine, longitudinal Safety population which includes, by age group:
 - a. the number and percentage of participants experiencing an AE leading to study withdrawal
 - b. the number and percentage of participants experiencing a SAE by maximal severity
 - c. the number and percentage of participants experiencing an MAAE
 - d. the number and percentage of participants experiencing a NOCD

The age groups referenced above are all participants, 21 to 55 years, and 56 to 80 years at the time of enrolment in the Parent Study.

NOTE: unsolicited AE that are not SAE, MAAE or NOCD are not collected in this study for participants in cohort 2 and are only collected up to 28 days after injection of ARCT-021 for participants in cohorts 1a and 1b. No participants received an off-study vaccine within the time window for collection of unsolicited AE that are not SAE, MAAE or NOCD, so no tabulation of all unsolicited events is being provided.

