5.3.3 Censoring

As participants in this study have, in many instances, received a COVID-19 vaccine that was not the designated investigational vaccine (“off study vaccine”) and receipt of a similar vaccine may influence

study interpretability, data will be censored at the time of receipt of this off study vaccine. Additional data collected past that day will be referred to as: Follow-up After Receipt of Off Study Vaccine.

Censoring Day is defined as:

- Date of first Off-Study Vaccine Dose - Study Day 1 + 1 for dates on or after date of Study Day 1.
- Date of first Off-Study Vaccine Dose - Study Day 1 if both doses of Off-Study vaccine were received prior to enrollment in ARCT-021-02.

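### SAP 8.1.9.3 names all ARCT-021 recipients as the population for events after off-study vaccine and does not restrict the denominator to off-study vaccine recipients, so its percentages are diluted unless uptake is complete

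*SAP*

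**What the plan says.** SAP 8.1.9.3 describes one summary of unsolicited treatment-emergent events "with onset after injection of off-study vaccine, longitudinal Safety population which includes, by age group". Its four rows cover AEs leading to withdrawal, SAEs, MAAEs and NOCDs. Each row is a count with a percentage; the SAE row, for example, is "the number and percentage of participants experiencing a SAE by maximal severity". The age groups are all participants, 21 to 55 and 56 to 80 years at Parent Study enrolment. No cohort split is given.

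SAP 5.2 defines the named population as "All participants who receive Study vaccine in either ARCT-021-01 or ARCT-021-02". It defines two other sets, the Safety Population and the Immunogenicity Population. Neither is conditional on off-study vaccine.

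On off-study vaccine use, SAP 5.3.3 begins: "As participants in this study have, in many instances, received a COVID-19 vaccine that was not the designated investigational vaccine". It gives no number and does not say that everyone received one. It labels the later data ("Additional data collected past that day will be referred to as: Follow-up After Receipt of Off Study Vaccine"), but this names a period of data and does not create an analysis set.

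The SAP's one explicit denominator rule is in 8.1.9.1, where incidence is obtained by "dividing the number of participants who have experienced the event by the total number of participants in the corresponding Cohort".

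**The concern.** An event after off-study vaccine can occur only in someone who received one. A participant who never did adds to the denominator and can never add to the numerator, so a percentage over all ARCT-021 recipients mixes the event frequency with vaccine uptake. The distortion can go only downwards, which is the reassuring direction.

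The section 8 introduction of the SAP lists unsolicited AEs, MAAEs and SAEs after off-study vaccine among the endpoints serving the primary safety objective, and 8.1.9.3 is the only adverse event summary table specified for that period. SAP section 4 says that this interim analysis supports a regulatory filing. A reader of the filing would naturally take the percentage as the frequency of events when another COVID-19 vaccine follows ARCT-021, and it would not be that.

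**Working it through.** The plan states no rate, uptake or sample size for this table, so there is no figure to reproduce. The check compares the two possible denominators.

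**Inputs from the documents**
- Population named for the table: all ARCT-021 recipients in either study (SAP 8.1.9.3 and 5.2).
- Possible enrolment: 106 (SAP 3.1); about 99, at most 166 (protocol 3.6).
- Off-study vaccine uptake: many participants, no figure (SAP 5.3.3).

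**Assumptions**
- Uptake share f = 25%, 50% or 75%.
- x = 5 participants with an event of a given type after off-study vaccine.
- N = the enrolled number.

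**Formulae.** With n = f × N recipients:
- percentage on the named population = x / N
- percentage among recipients = x / n
- so x / N = f × (x / n), and the understatement factor is N / n, or about 1 / f.

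**Results for N = 106, x = 5** (n rounded to whole participants)

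| Assumed uptake | n | 5 / 106 | 5 / n | N / n |
|---|---|---|---|---|
| 25% | 26 | 4.7% | 19.2% | 4.1 |
| 50% | 53 | 4.7% | 9.4% | 2.0 |
| 75% | 80 | 4.7% | 6.2% | 1.3 |

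The factor does not depend on x and hardly on N. For N = 99 (n = 25, 50, 74) it is 4.0, 2.0 and 1.3. For N = 166 (n = 42, 83, 124) it is again 4.0, 2.0 and 1.3. It equals 1 only at 100% uptake.

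**Two consequences**
- The same formula applies within each age group with that group's own uptake. If 10% of recipients had an event in both groups, but uptake were 75% in one and 25% in the other, the table would show 0.10 × 0.75 = 7.5% against 0.10 × 0.25 = 2.5%. All these values are assumed; the example shows only that uptake alone can create an apparent age difference.
- As worded, the Longitudinal Safety Population could include Parent Study vaccinees who never entered ARCT-021-02. If they were counted, N would be larger and the dilution greater.

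**The case against.** The strongest objection is that 8.1.9.3 states no denominator. It names a population and a condition on onset. The rule in 8.1.9.1 was written for the tables of that section and refers to a cohort, which this table does not have. The table shells are not in the documents and may show the number of recipients. This stands to the extent that one cannot say the SAP expressly prescribes a whole-population denominator. It does not remove the point: the only population named is the wrong at-risk set, no recipient set exists, and a programmer following the text would divide by everyone.

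A reader might infer more than the documents support:
- *That this is the only information on safety after another vaccine.* It is not. The section 8 introduction also plans vital signs for that period. SAP 8.1.4 to 8.1.7 provide listings with onset dates, grouped by cohort or sub-cohort, and individual narratives for SAEs, MAAEs, NOCDs and AEs leading to withdrawal.
- *That leaving out cohort is an error.* The main TEAE tables in 8.1.9.1 are by cohort and age, but no rule requires that here. Pooling is a defensible choice when about 106 participants, reduced to recipients, would be spread over three cohorts and two age groups.
- *That the size of the understatement is known.* It is not; uptake and event counts are both assumed above.
- *That the recipient percentage is the true rate.* It has the right people in the denominator but still ignores unequal follow-up time after the off-study vaccine.

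**Conclusion.** The point holds for one descriptive table. Followed as written, SAP 8.1.9.3 gives percentages of withdrawal AEs, SAEs, MAAEs and NOCDs after off-study vaccine that are understated by the factor 1 / f. That is about 4-fold to 1.3-fold for assumed uptake of 25% to 75%, and nil only at complete uptake. This rests on the plain reading that the named population supplies the denominator; if the shells already use recipients, all that is missing is a sentence saying so. Event counts are correct on either reading and no hypothesis test is affected. It is worth correcting because the table serves the primary safety objective, the error can only reassure, and the remedy is cheap.

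**What to change.** In SAP 8.1.9.3, state that the denominator is all participants with a recorded off-study vaccine date who have ARCT-021-02 safety follow-up after that date, and display that n overall and for each age group.

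The set should include participants vaccinated before enrolment in ARCT-021-02. SAP 5.3.3 provides for them, and exclusion criterion 3 in protocol 5.2 applies only to subjects who receive ARCT-021 in this study, so Cohort 2 may contain some. Requiring a vaccine date within this study's follow-up would wrongly leave them out of the denominator while their events could still be counted.

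Optionally, show the number of recipients and the event counts by Cohort 1a, 1b and 2, to match the main TEAE tables.

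The cost is one sentence and one table shell, since the off-study vaccine date is already needed for censoring. The downside is smaller denominators and less precise percentages. SAP 5.1 allows no change to the interim SAP once the data are pulled, so the edit should precede the pull; otherwise it should be applied at the final analysis.
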